1.2 DRUG PROFILE

1.2.1 BI 1358894

For a detailed description of the BI 1358894 profile, please refer to the current Investigator's Brochure (IB) [[c10354149](#)].

Pharmacokinetics in Humans

Human PK data are currently available from the FIM study 1402-0001, which consisted of an SRD part (tested doses: 3 mg – 200 mg BI 1358894) and of a food effect part (tested doses: 50 mg and 100 mg BI 1358894 under fasted and fed conditions) [[c24903142](#)].

Following oral administration of film-coated tablets in fasted state BI 1358894 reached maximum plasma concentrations after 1 to 5 hours. Thereafter BI 1358894 plasma concentrations declined in a multiphasic fashion implying multi-compartmental distribution and exhibited a long terminal phase, which seems to be dose-independent.

C_{max} , AUC_{0-72} and $AUC_{0-\infty}$ of BI 1358894 increased in a dose dependent way. Preliminary statistical evaluation showed that the increase in C_{max} and AUC_{0-72} was less than dose proportional. $AUC_{0-\infty}$ increased slightly less than dose proportional when given without food.

Also the food effect was dependent on the administered dose. While the exposure of BI 1358894 increased by factor 1.6 for the 50 mg dose, a food effect of factor 2.5 was observed for the 100 mg dose.

After completion of the food effect assessment, a dose of 200 mg BI 1358894 has been given after a high-calorie, high-fat meal in the SRD part of 1402-0001 [[c24903142](#)]. Compared to the cohort receiving 200 mg under fasted conditions, food increased exposure by about 2.4-fold (exposure of 200 mg BI 1358894, fed conditions: $C_{max} = 857 \text{ nM}$, $AUC_{0-24} = 11640 \text{ nM} \cdot \text{h}$).

Based on PK data of previous dose groups (DGs) in the 200 mg fed DG PK blood sampling was extended to 672 h. Sampling from 240 h to 672 h revealed another phase with low plasma concentrations and long terminal half-life of about 200 h. The proportion of AUC beyond 192 h is less than 20% of total AUC. Hence, it is not expected that this phase markedly contributes to accumulation or steady state attainment.

Preliminary PK data from the MRD study 1402-0002 [[c28667517](#)] support this observation. In the first dose groups (10 mg and 25 mg), an accumulation ratio (based on AUC_{0-24}) of 2.5 was observed. Steady state seems to be achieved after about 2 weeks. Both accumulation ratio and approximation of steady state attainment are in line with an effective half-life of ~50 to 70 h.

Safety and tolerability in healthy subjects

At the time of preparing this trial protocol, seven Phase I trials with administration of BI 1358894 to approximately 217 healthy subjects and 73 MDD patients have been conducted. Preliminary data on safety and tolerability observed in these trials are given below:

Proprietary confidential information © 2020 Boehringer Ingelheim International GmbH or one or more of its affiliated companies

1402-0001, SRD-part: In the SRD-part of the 1402-0001 study [[c24903142](#)], safety, tolerability, PK and PD of rising single doses of BI 1358894 has been investigated in 8 DGs (3 mg – 6 mg – 10 mg – 25 mg – 50 mg – 100 mg – 200 mg fasted – 200 mg fed) with planned 8 subjects (6 on active, 2 on placebo). The most frequent drug related AE was headache, which has been reported by 18 of 48 subjects on active treatment. While headache occurred in 50% of subjects on active treatment in DG 2 and in DG 5-8, it was reported by only 1 subject in DG 1 and by 2 subjects in DG 4. The intensity of headache was mild (16 x) to moderate (2 x). The two cases of moderate headache have been observed in DG 5 and 7.

Beyond headache the following drug-related AEs have been observed (each in 1 subject only): delayed auditory perception, dizziness, head pressure, back pain, lightheadedness, tiredness and loss of concentration. These AEs were of mild to moderate intensity.

1402-0001, food effect part: This part of the 1402-0001 study [[c24903142](#)] investigated the effect of food on the kinetics of 50 mg (N=8) and 100 mg (N=12) BI 1358894, given as a single dose in two trial periods. The most frequent drug related AE was headache, which has been reported by 15 of 20 subjects (in nine subjects drug related headache occurred in both trial periods).

Beyond headache the following drug-related AEs have been observed: dizziness (5 subjects), tiredness (3 subjects), lightheadedness (2 subjects), loss of concentration (2 subjects), and meteorism, back pain, intermittent hip pain, head pressure, exacerbation of face acne and skin irritation with itching at the whole body (1 subject each). All drug related AEs were of mild or moderate intensity.

1402-0002, MRD-study: Trial 1402-0002 [[c28667517](#)] investigated safety, tolerability, PK and PD of rising multiple doses BI 1358894 (administered over 14 days) in a double-blinded fashion in a total of five DGs (10 mg, 25 mg, 50 mg, 100 mg and 200 mg) with a total of 50 subjects (40 on active, 10 on placebo) has been already finished.

Overall, the most frequent drug related AE is headache which has been reported by 17 of 40 subjects. Frequency of drug related headache was not dose-dependent and was even less frequent in higher DGs (50 mg, 100 mg). Drug-related headache was mainly of mild intensity. Moderate intensity has been reported only for three subjects in DG 2 (2 x) and DG 4 (1 x).

In the 25 mg DG seven from ten subjects reported drug related headache. In four cases the affected subjects suffered from intermittent headache that lasted over 9-12 days. In one subject this was accompanied by drug related nausea on Day 6 and 9. Due to this continuous impairment the subject withdrew informed consent prior to dosing on Day 10.

Beyond headache the following drug-related AEs have been observed: orthostatic dysregulation (6 subjects), dizziness (5 subjects), tiredness (3 subjects), heartburn (2 subjects) and stomach cramps, blurred vision, acneiform skin (face), nausea, loose stool, flatulence, decreased concentration, head pressure, fasciculation (finger), and pressure on both eyes (1 subject each). These AEs were of mild intensity and did not follow a specific pattern of distribution.

1402-0003: Trial 1402-0003 [[c28123801](#)] investigated the effect of a single dose of BI 1358894 compared to placebo on BOLD responses in modulation brain processing of emotional and cognitive stimuli on the amygdala and related brain structure using fMRI in

Proprietary confidential information © 2020 Boehringer Ingelheim International GmbH or one or more of its affiliated companies

unmedicated patients with depression in a randomized, placebo-controlled, parallel-group study. Overall, 73 patients with MDD (males and females) were treated either with BI 1358894 (25 patients), with citalopram (24 patients) used as a positive control, or placebo (24 patients).

The overall summary showed that there were no deaths and SAEs. There were also no reports of AESIs, severe AEs, AEs leading to discontinuation of trial drug, or other significant AEs. The frequency of patients with any AEs was higher in the BI 1358894 treatment group (23 patients) than in the citalopram (15 patients) and placebo (14 patients) groups. The most common AE was headache. In the BI 1358894 treatment group, headache was reported by 17 patients compared with 13 patients in the citalopram and 10 patients in the placebo groups.

Overall safety results from trial 1402-0003 [[c28123801](#)] are in line with the safety results of Phase I trials.

1402-0005: Trial 1402-0005 [[c28698771](#)] investigated the pharmacodynamic effects of a single dose of BI 1358894 on CCK-4 induced anxiogenic/panic-like symptoms using the Panic Symptom Scale (PSS) in preselected CCK-4 sensitive healthy volunteers in a double-blind, randomized, placebo-controlled, crossover study. In this trial, 20 patients were treated with a single dose of 100 mg BI 1358894 and placebo (10 patients in the sequence BI 1358894, placebo; 10 patients in the sequence placebo, BI 1358894).

The overall summary showed that there were no deaths and SAEs. There were also no reports of AESIs, AEs leading to discontinuation of trial drug, or other significant AEs. The most common AE was headache and was most frequently reported in the BI 1358894 treatment group (10 subjects) than in the placebo group (1 subject).

Overall, the results of Trial 1402-0005 [[c28698771](#)] are in line with the pooled safety analysis of Phase I trials.

1402-0007: Trial 1402-0007 [[c28714279](#)] investigated the effect of the CYP3A4 inhibitor itraconazole on the kinetics of the CYP3A4 substrate BI 1358894 in 16 healthy subjects. A single dose of 10 mg BI 1358894 has been given alone and together with multiple doses of itraconazole. The most frequent drug related AE was headache reported by five subjects. In one case headache was of severe intensity. All subjects completed the trial.

1402-0009: Trial 1402-0009 investigated the relative bioavailability of rosuvastatin (Part 1) and dabigatran (Part 2) given alone and together with BI 1358894 in 28 healthy male subjects (14 in each part). Final results are not yet available at the time of CTA, however no safety findings in conflict with previous observations were reported.

1402-0010: Trial 1402-0010 [[c28907328](#)] investigated the relative bioavailability of different trial formulations of BI 1358894. The 24 participating subjects had to undergo three treatment periods. In each trial period a single dose of 100 mg BI 1358894 has been administered. The most frequent drug related adverse event was headache, that has been reported by about 50% of subjects. Drug related dizziness and tiredness was reported by two subjects each. All drug related adverse events were of mild or moderate intensity.

For a more detailed description of BI 1358894, please refer to the current Investigator's Brochure (IB) [[c10354149](#)].

1.2.2 Residual Effect Period

Based on an effective half-life of 50 to 70 h the Residual Effect Period (REP) of BI 1358894 has been determined to be 14 days. This is the period after the last dose with measurable drug levels and/or pharmacodynamic effects is still likely to be present.

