10.2 RADIATION BURDEN CALCULATION

Radiation Burden Calculation Report
BI 1354149

Radiation Burden Calculation Report

Title:	BI 1358894 hADME - Radioburden Calculation
Sponsor:	Boehringer Ingelheim
Protocol No:	BI 1358894
PRA Project Id:	TBD
Version Date:	27 Feb 20

Calculation of Radiation Burden (Dosimetry)

BI 1358894 is an inhibitor of 2 transient receptor potential canonical (TRPC) channels, which are TRPC4 and TRPC5. BI 1358894 is being developed for the treatment of major depressive disorder (MDD) and borderline personality disorder (BoPD).

Excretion and pharmacokinetic studies using BI 1358894 were conducted on rats^{1,2}, and quantitative tissue distribution studies on pigmented and non-pigmented rats³. A radiation dose assessment was made based on these studies. In addition, data from studies in human patients⁴ were taken into consideration.

The following assumptions, based on the data from these experiments, and taking the worst-case scenario, were made to be able to estimate the effective radiation dose:

- After oral dosing, BI 1358894 and possible metabolites are considered to be distributed more or less homogeneously throughout the body, with the exception of higher exposure of the liver and brain, which are calculated separately.
- The major part of the administered amount of ¹⁴C-radiolabeled BI 1358894 and possible metabolites show reasonably fast elimination from the body, almost completely via fecal excretion.
- Using the data of the BI 1358894 study in rats a half-life of total ¹⁴C-activity of 120 hours is estimated, in humans a terminal phase half-life of BI 1358894 of approximately 960 hours is assumed⁴.
- The absorbed fraction is 0.8, based on rat data¹.
- Based on the excretion study in rats ¹⁴C-radiolabeled BI 1358894 is found to be excreted both in feces and in urine. For the calculation is assumed: 100% of the administered radioactivity is excreted via the gastrointestinal tract in feces.

Based on these assumptions the estimated effective radiation burden after a single oral radioactivity dose of 3.7 MBq ¹⁴C-radiolabeled BI 1358894 is approximately 0.51 mSv. For biomedical investigations in small groups of human volunteers an effective dose of 0.1 – 1.0 mSv is considered acceptable⁵.

References:

- 1: preclinical report A117/16SMB (B5853) Excretion of radioactivity in urine, faeces and bile after oral and intravenous administration of [14C]BI 1358894 to rats, (dated 15 November 2016)

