10.3 COVID-19 SITE SPECIFIC MEASURES

This section contains a risk assessment for study 1402-0015 with BI 1358894 due to the circumstances created by the coronavirus disease-19 (COVID-19) pandemic. In addition, the document summarizes the mitigation approaches to be followed to minimize the risk of spreading severe acute respiratory syndrome coronavirus 2 (SARS CoV-2).

Risk Assessment

BI 1358894 is a TRPC4/5 inhibitor in development for treatment of Major Depressive Disorder and for the treatment of Borderline Personality Disorder (BoPD). It is expected that treatment with BI 1358894 has the potential to improve affective symptoms and emotion control, especially in patients with MDD who inadequately respond to the current standard of care (SSRI; SNRI) and in patients with BoPD, where no approved drug treatment is currently available

Relevant information on the product

BI 1358894 is a highly potent and selective TRPC4/5 Inhibitor (transient receptor potential cation channel, subfamily C, members 4 and 5). It has the potential to address core symptoms of MDD and BoPD as it targets TRPC4/5 ion channels. TRPC4 and TRPC5 are highly expressed in pyramidal neurons of the amygdala in the frontal cortex, hippocampus, and hypothalamus, brain areas that are involved in circuits contributing to emotional control. BI 1358894 is thought to decrease neuronal excitability leading to normalization of the activation state of limbic circuits, which are known to be important for emotional control.

BI 1358894 is characterised by high bioavailability after oral intake, moderate volume of distribution, low clearance and long terminal half-life. Excretion occurs almost exclusively via faeces. After administration of BI 1358894 tablets, maximum plasma concentrations of BI 1358894 occurred around 1 to 5 hours after dosing. The terminal half-life was 41 to 52 hours for blood. Steady state was reached after 11 to 14 days of BI 1358894 dosing.

Currently, repeat dose toxicity studies up to 13 weeks revealed toxicologically relevant effects on the skin (mice), Harderian glands (mice), hepatic function (mice), the vascular system (rats), male genital tract (rats), the Central Nervous System (CNS) function (dogs), and the digestive tract, renal function, and white blood cell parameters (mice, rats and dogs).

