6. GENERAL ANALYSIS DEFINITIONS

6.1 TREATMENTS

For basic study information on treatments to be administered, assignment of treatment groups, and selection of doses, cf. Section 4 of the CTP.

The trial consists of Part 1 and Part 2 and the two parts will be analysed separately.

In Part 1, subjects are planned to be treated with a single dose of BI 1358894 mixed with [14C] BI 1358894.

For statistical analyses of AEs, safety laboratory data, and vital signs the following separate analysis phases will be defined for each subject:

Table 6.1: 1 Part 1 - Analysis phases for statistical analysis of AEs, safety laboratory data and vital signs

Study analysis phase	Label	Start (inclusive)	End (exclusive)
Screening	Screening	Date of informed consent	Date/time of administration of study drug
On-treatment	BI 1358894 SD	Date/time of administration of study drug	Date/time of administration of study drug + REP (14 days * 24 h)
Follow-up	F/U BI 1358894 SD	Date/time of administration of study drug + REP (14 days * 24 h)	12:00 a.m. on day after trial completion date

SD = Single Dose

In Part 2, subjects are planned to be treated with multiple dose of 100 mg BI 1358894 as 2 film-coated tablets once daily (2 tablets x 50 mg, q.d.) from Day 1 to Day 21.

Table 6.1: 2 Part 2 - Analysis phases for statistical analysis of AEs, safety laboratory data and vital signs

Study analysis phase	Label	Start (inclusive)	End (exclusive)
Screening	Screening	Date of informed consent	Date/time of first administration of study drug
On-treatment	BI 1358894 MD	Date/time of first administration of study drug	Date/time of last administration of study drug + REP (14 days * 24 h)
Follow-up	F/U BI 1358894 MD	Date/time of last administration of study drug + REP (14 days * 24 h)	12:00 a.m. on day after trial completion date

MD = Multiple Doses

AE displays in CTR Section 15.3, Appendix 16.1.13.1.8.2 and Appendix 16.1.13.1.8.3 will present results for the on-treatment phase only.

More details on the technical implementation of these analyses are provided in the ADS Plan of this TSAP.

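### The 2.5-fold accumulation does not fit the 50–70 h effective half-life; separately, the 14-day residual effect period keeps later adverse events out of the summary tables although drug is probably still measurable.

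*Protocol*

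**What the plan says.** **Half-life.** Protocol Section 1.2.1 gives preliminary results from the multiple-rising-dose study: "In the first dose groups (10 mg and 25 mg), an accumulation ratio (based on AUC_{0-24}) of 2.5 was observed". It adds that steady state seems to be reached after about two weeks, and concludes: "Both accumulation ratio and approximation of steady state attainment are in line with an effective half-life of ~50 to 70 h". Section 1.4 confirms once-daily dosing in that study.

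**REP.** Section 1.2.2 sets the length: "Based on an effective half-life of 50 to 70 h the Residual Effect Period (REP) of BI 1358894 has been determined to be 14 days". It then defines the term: "This is the period after the last dose with measurable drug levels and/or pharmacodynamic effects is still likely to be present".

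**Late phase.** Section 1.2.1 reports on the group given a single 200 mg dose with food: "Sampling from 240 h to 672 h revealed another phase with low plasma concentrations and long terminal half-life of about 200 h". It puts less than 20% of total AUC beyond 192 h and expects little effect on accumulation. Two appendices give other terminal half-lives. Section 10.3 says: "The terminal half-life was 41 to 52 hours for blood". Section 10.2 says: "in humans a terminal phase half-life of BI 1358894 of approximately 960 hours is assumed". Section 10.3 also expects the drug to be eliminated by the follow-up examination, which in Part 1 can fall as early as Day 16.

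**Use in the analysis.** SAP Tables 6.1:1 and 6.1:2 end the on-treatment phase 14 × 24 h after the (last) dose. SAP Section 6.1 says that the AE displays in CTR Section 15.3 and two appendices "will present results for the on-treatment phase only". SAP Section 7.8.1 summarises headache that starts on treatment and only lists headache that starts in follow-up.

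**The concern.** An effective half-life describes accumulation. How long drug stays measurable depends on the terminal phase and the assay limit. The REP takes its length from the first and part of its definition from the second, and the protocol's own late-phase data suggest that the two differ here. The ratio quoted in support of the effective half-life does not reproduce it either.

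What is at stake is the content of the safety tables. Protocol Section 7.1 names safety and tolerability as a further objective. With 8 subjects per part, a few late events would visibly change a summary. Headache is the most frequent drug-related AE in most of the earlier trials described in Section 1.2.1. No primary or secondary endpoint is affected.

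**Working it through.** **1. Does a ratio of 2.5 give 50–70 h?**

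Inputs: R = 2.5 (Protocol 1.2.1); dosing interval 24 h (Protocol 1.4). For single-exponential decline, R = 1/(1 − 2^(−24/t)), so t = 24 × ln 2 / ln(R/(R − 1)).

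- R = 2.5: t = 16.64 / ln(2.5/1.5) = 16.64 / 0.511 = 32.6 h.
- t = 50 h: R = 1/(1 − 0.717) = 3.53.
- t = 70 h: R = 1/(1 − 0.788) = 4.73.
- After 14 doses rather than at full steady state, 50 and 70 h still give R = 3.50 and 4.56.

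Variants for R = 2.5:

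- Rounding of R (2.45–2.55): 31.7–33.4 h.
- First-order absorption with an assumed absorption half-life of 0.5–2 h: 31.6–28.5 h.
- The approximation t = ln 2 × 24 × R: 41.6 h.

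None reaches 50 h.

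**2. Does time to steady state give 50–70 h?**

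Taking 4–5 half-lives as the usual approach to steady state:

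- 50–70 h: 4 × 50 h = 8.3 days to 5 × 70 h = 14.6 days, which fits about two weeks.
- 32.6 h: 5.4–6.8 days, which does not fit.

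The two supports therefore point to different half-lives.

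**3. Does the REP follow from its stated basis?**

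14 days = 336 h.

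- At 50–70 h: 336/50 = 6.7 and 336/70 = 4.8 half-lives. The plan's figure is reproduced.
- At 32.6 h: 336/32.6 = 10.3 half-lives.

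Correcting the half-life downwards would make 14 days look more generous, so the discrepancy in step 1 does not shorten the REP.

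**4. Does the REP fit its definition?**

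Input: terminal half-life about 200 h, from 240–672 h sampling (Protocol 1.2.1).

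- 336/200 = 1.7 half-lives, so 2^(−1.68) = 31% of that phase's starting level remains at the end of the REP.
- Relative to 240 h, the level at 336 h is 2^(−96/200) = 72%.
- 240–336 h spans 96/200 = 0.48 of a half-life. A 200 h estimate would be hard to obtain without quantifiable samples later than that. This is an inference; the protocol does not state it.
- In Part 2 the last plasma sample is on Day 62, (62 − 21) × 24 = 984 h after the last dose, close to 5 × 200 = 1,000 h.

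**5. What falls outside the AE displays?**

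- Part 2: the last dose is on Day 21, so the on-treatment phase ends on Day 35. Follow-up to Day 62 covers 27 of the 41 days after the last dose. The flow chart has 10 post-discharge AE contacts (Days 30, 34, 37, 41, 44, 48, 51, 55, 58 and 62); 8 of them fall after Day 35.
- Part 1: the on-treatment phase ends on Day 15. Follow-up can run to Day 50, up to 35 days.

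**The case against.** Several counter-arguments stand and limit the point.

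- **The drug is multiphasic.** The formula in step 1 assumes one exponential. A multiphasic drug can combine modest accumulation with a slow approach to steady state. The ratio is also preliminary and comes only from the 10 and 25 mg groups. This may explain the mismatch, but then no single half-life is supported by both observations, and the text should say how 50–70 h was obtained.
- **Restating the half-life as 33 h would not settle it.** That would contradict steady state at about two weeks in the same section.
- **Measurability is not shown for these regimens.** The late phase was seen after 200 mg with food, at low concentrations. Part 1 gives 100 mg fasted as a solution, and food raised 200 mg exposure about 2.4-fold. No plasma assay limit is given for the parent drug. The definition also says and/or, although no pharmacodynamic basis for 14 days is offered.
- **The late phase may matter little clinically.** Less than 20% of AUC lies beyond 192 h, and the sponsor considered this.

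A reader might also infer four stronger things that the documents do not support:

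- That late AEs are lost. Protocol Section 5.2.6.2.1 collects them to each subject's end of trial, and SAP Section 7 lists all individual values.
- That Section 3.3.4 stops AE questioning of discontinued subjects at 14 days. It asks for contact at or after the end of the REP, which is a minimum.
- That drug was shown to be measurable up to 672 h. The text describes sampling over that window and does not say that the last samples were quantifiable.
- That 960 h is a rival estimate. Section 10.2 presents it among worst-case assumptions for dosimetry.

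**Conclusion.** Both points hold, independently of each other.

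(a) A ratio of 2.5 implies about 33 h, not 50–70 h, which would need about 3.5–4.7. This assumes single-exponential accumulation at a 24 h interval. It is an inconsistency in the background text. It would be tempting to conclude that it makes the REP too short, but it does not.

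(b) Drug is likely to remain measurable after 336 h, most clearly after 21 daily doses in Part 2. The exact duration cannot be computed without the assay limit. As a result, Part 2 AEs with onset on Days 35–62 are collected and listed but absent from the summary displays, and follow-up headache is listed only.

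The like-for-like conflict between terminal half-lives is 41–52 h (Section 10.3, stated for blood) against about 200 h (Section 1.2.1, plasma). The expectation in Section 10.3 that the drug is eliminated by follow-up sits poorly with the latter, especially for a Part 1 examination near Day 16.

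**What to change.** - **SAP Sections 6.1 and 7.8.1:** add the follow-up phase, and an on-treatment plus follow-up total, as columns in the CTR Section 15.3 AE tables. Summarise follow-up headache in the same way.
- **Protocol Section 1.2.2:** align the wording of the REP definition with its effective half-life basis.
- **Protocol Section 1.2.1:** check the ratio of 2.5, or state how 50–70 h was derived for a multiphasic drug.
- **Protocol Sections 1.2.1 and 10.3:** reconcile about 200 h with 41–52 h, together with the statement that the drug is expected to be eliminated at follow-up.

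The cost is some wording and extra table columns, in which a few late and probably unrelated AEs will appear. No new data are needed.

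Resetting the REP itself to 672 h or more is not recommended on this evidence. It would lengthen the contact period for discontinued subjects. It would also outlast the end-of-trial visit of Part 1 subjects released on Day 15, which is due within 7 days (by Day 22), whereas 672 h is Day 29.
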